## Division & Personnel

### Division

What Division/Department does the PI belong to?

Division on Substance Abuse, Department of Psychiatry

Within the division/department, what Center or group are you affiliated with, if any?

n/a

## Procedures

To create the protocol summary form, first indicate if this research will include any of the following procedures

- ✓ Psychiatric Assessment
- ✓ Collection of Biological Specimens
- ✓ Medication Trial
- ✓ Use of Placebo or Sham Treatment
- ✓ Biological Challenge Procedure
- ✓ Use of Investigational Drug or Device

## Population

Indicate which of the following populations will be included in this research

- ✓ Medically and Psychiatrically Healthy Subjects
- ✓ Adults
- ✓ Adults over 50
- ✓ Substance Users

## Research Support/Funding

Will an existing internal account be used to support the project?

No

Is the project externally funded or is external funding planned?

Yes

Select the number of external sources of funding that will be applicable to this study

Funding Source #1

Is the PI of the grant/contract the same as the PI of the IRB protocol?

Yes

Select one of the following

The grant/contract application is a pending review or a funding decision

Source of Funding

Federal

Institute/Agency

---

National Institute on Drug Abuse

**Grant Name**

Neuropeptide modulation of stress: a novel approach to cocaine relapse

**Grant Number**

pending+

**Select one of the following**

Multicenter (NYSPI is a participating site)

**Business Office**

RFMH

**Does the grant/contract involve a subcontract?**

No

**Study Location**

**Indicate if the research is/will be conducted at any of the following**

NYSPI

**This protocol describes research conducted by the PI at other facilities/locations**

Yes

Hospital, clinics and other healthcare facilities

**Lay Summary of Proposed Research**

**Lay Summary of Proposed Research**

This proposal describes a combined laboratory and clinical trial preliminary investigation to advance medication development for cocaine dependence. The main objective is to test whether intranasal oxytocin could reduce relapse risk by reducing stress sensitivity. To measure stress sensitivity, this study will evaluate a new stress challenge: a) intranasal desmopressin, a vasopressin analog, will be used as an endocrine stressor; its effects will be evaluated by serial measurements of serum Adrenocorticotropin hormone

---

(ACTH), and self reports; b) if pretreatment with intranasal oxytocin dampens the ACTH and subjective response to intranasal desmopressin. These measures will be tested during a 7-day inpatient abstinence induction hospitalization. For those patients with family and work obligations, an outpatient abstinence induction procedure is available. The response to the desmopressin challenge will be compared to a cohort of matched control subjects. After abstinence induction, cocaine dependent patients enter a 6-week, double-blind, randomized, placebo-controlled trial of 24 IU of intranasal oxytocin vs. placebo, to monitor if this reduces the relapse risk.

This study is based on the findings that chronic stress, caused in these patients by cocaine dependence, increases the sensitivity of the Hypothalamo-Pituitary-Adrenal (HPA) axis and CNS stress pathways to vasopressin. For their part, oxytocin systems, in chronic stress, acquire an increasing moderating effect on CNS stress systems and the HPA axis. Cocaine dependence generates increased responsivity of stress systems to oxytocin in the face of depleted oxytocin stores; thus creating an environment where exogenous oxytocin could exert a strong regulatory effect. Intranasal administration provides a convenient to deliver these small peptides to the brain. Studying the feasibility of this approach, and its applicability to the treatment of cocaine-dependent patients, will be a goal of this study.

The main outcome of this study will be the number of consecutive days of abstinence from cocaine after abstinence induction. A secondary outcome will be whether the acute effect of intranasal oxytocin on desmopressin-induced ACTH secretion is associated with the number of days of continued abstinence.

## **Background, Significance and Rationale**

### **Background, Significance and Rationale**

Human laboratory studies have reliably shown that stress induced by psychological, endocrine, or cue-related challenges cause craving for cocaine that predicts relapse (Sinha et al., 2006; Brady et al., 2009; Back et al., 2010). The conditioning tying together stress and relapse to cocaine use hinges on new patterns of stress regulation provoked by repeated use of the drug (Koob, 2008). Cocaine-dependent patients experiencing stress report greater anxiety, restlessness, cravings

---

(Bergquist et al., 2010), and secrete more ACTH and cortisol than control subjects (Sinha et al., 2006). These adaptations sustain the addiction and undermine efforts by patients to end it.

Attempts to develop medications of sufficient efficacy to treat cocaine addiction have so far failed (Taylor & Gold, 1990; Bisaga et al., 2005; Bisaga et al., 2010). Given the role of stress in perpetuating cocaine dependence, medications that corrode the conditioned link between stress and cocaine use could be prototypes for medication developments. Such a prototype may involve Vasopressin (VP) and Oxytocin (OT), neuropeptides physiologically and anatomically poised to influence the stress response. The relevance of VP and OT to cocaine addiction relates to their role in the sensitization of stress and reward brain circuits to chronic cocaine exposure.

### *1.1 Neuropeptides, Vasopressin, Oxytocin: basic concepts.*

The history of neuropeptides begins with VP and OT. Du Vigneaud and his team deduced the structure of VP and OT, and synthesized each in 1954 (du Vigneaud, 1954). These peptides are old in phylogeny (going back 500 million years), have evolved together, are found in all vertebrates, and are early joint regulators of homeostasis; which required that the effect of one could counterpoise the effect of the other (Van Kesteren et al., 1992). OT and VP are synthesized within neurons from a single precursor: then, a cascade of processes determine its biological activity through size, form, and derivation of the end product, generating peptides with different, and at times, opposite effects (de Wied et al., 1993).

VP is the hormonal regulator of water homeostasis (Arimura et al., 1967). With Angiotensin, it governs drinking behavior (Severs et al., 1977). The hormone OT regulates parturition and lactation (Higuchi et al., 1986). It also promotes sexual, reproductive, social, and nurturing behaviors (Pedersen et al., 1979), on which VP exerts mostly a temporizing effect (de Wied et al., 1993). This intricate webbing of behavioral and physiological effects is a feature of hypothalamic neuropeptides. Another feature is reflected in their effect on single neurons: VP and OT can exert lasting influences (Kombian et al., 2002) on neurons at CNS sites controlling homeostasis (Buijs et al., 1983). For example, OT or VP affect 2nd messenger systems (Manning et al., 2008), influence the effects or the release of primary neurotransmitters such as glutamate (Joels and Urban, 1982; Van den Hooff and Urban, 1990), and can generate ionic currents (Dreifuss and Raggenbass, 1992) that induce Long-Term-Potential, an inducible neuronal activity that underlie behavioral adaptations and learning (Teyler and Discenna, 1987). Many of these effects outlast the functional half-lives of OT or VP.]

### *1.2. Vasopressin, stress, cocaine dependence, and why a new stress challenge?*

---

Vasopressin and OT are nonapeptides that differ from each other by only 2 amino acids. Yet, this small difference imparts VP and OT with greatly demarcated effects on the stress response involving the Hypothalamo-Pituitary-Adrenal axis (HPA). The HPA response begins with Corticotropin Releasing Factor (CRF) containing neurons in the Paraventricular Nucleus of the hypothalamus (PVN). These CRF neurons receive stimuli from afferents that signal physiological, sensory, or behavioral disturbances. Upon release of CRF, corticotrophs in the adenohypophysis secrete Adrenocorticotrophic Hormone (ACTH) that stimulates the adrenal glands to secrete glucocorticoids, which moderate the secretion of CRF and ACTH (Koob, 2008).

Compared to CRF, VP by itself exerts a weak effect on ACTH secretion. Once CRF had been characterized as the major factor regulating ACTH secretion (Vale et al., 1981), it was rapidly noted that exposure of corticotrophs to CRF and VP provoked greater ACTH release than either peptide alone, raising a possibility that CRF and VP may be co-localized in the same PVN neurons (Rivier & Vale, 1983). This was confirmed, and found to depend on the chronicity of stress. In animals, more VP RNA and VP was found in the soma of a greater proportion of CRF neurons, and VP was co-localized with CRF in neurosecretory axon terminals (de Goeij et al., 1991, 1992). Chronic stress thus induces a shift from CRF to VP-controlled HPA activation: in the PVN, CRF mRNA levels decrease and VP mRNA levels increase; in the adenohypophysis, CRF receptor density decreases while VP1b receptor density increases, a mechanism by which the HPA maintains its activity in the face of persistent glucocorticoid release and down regulation of CRF and CRF receptors (Scott & Dinan, 1998; Ducat et al., 2012). These adaptations in the PVN and anterior pituitary are found in human subjected to chronic stress (Araya et al., 2006), and have been reproduced in animal models of drug addiction. For example, VP facilitates the development of tolerance to morphine and alcohol (Colbern et al., 1986); withdrawing cocaine from rats exposed to a 14-day escalating "binge" cocaine dose caused secretion of high levels of ACTH and corticosterone that could be blocked by a V1b receptor antagonist. It also increased VP mRNA in the PVN without concurrent increase in CRF mRNA, and increased V1b receptors in the pituitary (Zhou et al., 1996, 2011). Hence, endocrine adaptations to cocaine dependence and other drugs involve VP-based mechanisms, and the evidence for this supports the plausibility of the endocrine challenge with the VP analog desmopressin proposed herein. In support of this approach, two reports present data showing that the VP analog desmopressin (DDAVP) provoked greater ACTH release in human subjects with another condition related to chronic stress: chronic major depression (Dinan et al., 2004; Araya et al., 2006).

Stress sensitivity and its dysregulation are subject to individual genetic, constitutional and environmental factors (Kreek and Laforge, 2007). These factors impact treatment. Cocaine-dependent patients at baseline, with an abnormal diurnal cortisol secretion profile (48% of the sample), could not become abstinent from cocaine during a lead-in of a clinical trial ([name] et al., 2013, accepted). Therefore, it is reasonable to think that some cocaine-dependent patients - with similar severity of cocaine use - differ in terms of stress sensitivity or dysregulation. Because of this, they may face very different odds of overcoming their addiction. A VP challenge might reveal a form of stress dysregulation related to cocaine use in humans, and provide some answer to this question: Is high stress sensitivity or dysregulation a necessary condition for a positive outcome from OT, from other treatments targeting stress; or could it be applied to anyone with cocaine dependence seeking treatment?]

---

### *1.3. Oxytocin, the stress response, and its pertinence to cocaine dependence.*

The adaptations of the OT system in chronic stress occur in tandem with those of the VP system but differ. In animal models of HPA regulation, OT appears to act as a VP antagonist (Hartwig, 1989). Intracerebro-ventricular (icv) infusion of an OT antagonist disinhibits the HPA axis (Neuman et al., 2000b) and OT reduces stress hormone release during acute and recurrent stressors (Ditzen et al., 2009). The OT innervation and receptors responsible for restraining the stress and HPA response reside within the PVN, on and surrounding the CRF/VP neurons responsible for HPA activation (Dabrowska et al., 2011); and in more distant sites such as the amygdala and lateral septum that are richly endowed with glucocorticoid receptors (Fuxe et al., 1985). Glucocorticoid binding to these receptors induces up-regulation of OT receptors (Liberzon et al., 1997). The OT system is thus positioned to display increasing inhibitory effects on the stress response as a stressor becomes more chronic (Windle et al., 2004). However, the CNS pathology induced by drug addiction may break this process of homeostatic protection.

In one animal and one human study, recurrent cocaine or alcohol use was reported to deplete OT stores in the hypothalamus, hippocampus, and amygdala (Sarnyai et al., 1992; Sivukhina et al., 2006). Consequently, cocaine dependence may create a hormonal environment in which this regulatory mechanism cannot fully operate due to decreased OT stores. As this hormonal environment also favors upregulation of OT receptors (see above), it could be surmised that OT pathways would be especially sensitive to exogenous OT. If this were so, favorable conditions would exist to test if IN OT can reduce stress sensitivity and the relapse risk inherent to cocaine dependence. In support of this notion, effects of OT on addiction-related behaviors have been reported: exogenous OT in rodents retarded the development of alcohol or opiate tolerance (Colbern et al. 1986); it also decreased the hyperactivity, locomotor sensitization and stereotyped behavior caused by cocaine; and inhibited metamphetamine-induced place preference, facilitated its extinction, and inhibited its reinstatement by stress (Kovacs et al., 1990; Sarnyai & Kovacs, 1994; Qi et al., 2008, 2009).

Exogenous IN OT could also exploit another feature of OT systems of potential pertinence: the autocrine and paracrine effects of OT on OT neurons. Chronic stimulation of OT receptors by OT leads to anatomical and physiological changes in OT neurons that sustain OT release (Ludwig & Leng, 2006). Therefore, once OT systems are triggered with sufficient constancy, they display a proclivity to sustain OT secretion for extended periods of time. This would adequately serve instances of prolonged need such as lactation (Theodosios, 2002), and could prove advantageous for the treatment of a chronic, relapsing condition like cocaine dependence. While gender differences have been documented for some effects of OT; as a regulator of the CNS stress response and of the HPA axis, OT appears to play an equally important role in male and females (Neumann et al., 2000a, b). Nonetheless, we will investigate gender differences (exploratory aim b).

### *1.4 Intranasal administration, Desmopressin, Oxytocin, and Pharmacological Properties.*

The intranasal (IN) route of administering neuropeptides is a validated and approved method of drug administration in the pharmacological industry. The FDA has approved the medicinal use of

IN VP, and of its analogue desmopressin (DDAVP), and IN OT is approved in Europe (Syntocinon, 2012; Baumgartner et al., 2008). Although vascular brain areas devoid of blood-brain barrier (BBB) allow for some CNS penetration, systemic delivery of therapeutics to the CNS is not effective for 98% of small molecules (Pardridge, 2005). The IN route allows delivery of small peptides such as DDAVP and OT from the nasal mucosa to the brain via intraneural (olfactory and trigeminal nerves) and perivascular pathways (Dhuria et al., 2010), with sustained levels of VP, DDAVP, and OT being measured in the CSF hours after IN administration (Born et al., 2002; Dhuria et al., 2010; Linnen et al., 2011).

DDAVP will be the agonist used in this study because it is a longer-lasting agonist at the human V1b receptor (V1b > >V1a in the CNS; Bielsky et al., 2004), has little affinity for the peripheral V2 (renal) and V1a (vascular) receptors, and has no affinity for the OT receptor (Saito et al., 1997). When given IV, at recognized doses (80 IU) DDAVP does not cross the BBB, but has good CNS penetration by the IN route (Stegner et al., 1983; Manning et al., 2008). IN OT is not euphorogenic and is not reported to be distinguished from placebo in control subjects at doses proposed in this study (20 IU; Macdonald et al., 2011). Presently, there are no synthetic OT receptor agonists or V1b receptor antagonists available for human use (Manning et al., 2012). Should these become available, these would be attractive prototypes for medication development.

References for this section can be found in the uploaded grant application.

## Specific Aims and Hypotheses

### Specific Aims and Hypotheses

**Primary Aim 1 [Phase 1]:** The goal of primary aim 1 is to investigate the effect that both IN DDAVP and OT have on stress sensitivity. *Primary Aim 1a, hypothesis 1:* IN DDAVP will be associated with greater secretion of ACTH and subjective ratings in cocaine dependent patients compared to control patients. *Primary Aim 1b, hypothesis 2:* IN OT treatment will significantly reduce the secretion of ACTH and subjective ratings associated with IN DDAVP in cocaine dependent patients compared to control patients. The differences based on the outcomes specified in hypotheses 1 and 2 between the subjects in COC and CON groups will be examined

using parametric or non-parametric matched sample test.

**Primary Aim 2 [Phase 2]:** The goal of primary aim 2 is to investigate the effect of OT on cocaine use after abstinence induction. Primary Aim 2, hypothesis 1: Cocaine-dependent patients receiving IN OT will display significantly more days of consecutive abstinence after abstinence induction compared with IN placebo at the end of the study. The effect of IN OT treatment (based on groups) on the primary outcome (maximum number of consecutive abstinence days for each patient) will be analyzed using generalized linear models (PROC GLIMMIX in SAS®) with main effect of randomization assignment (OT vs. PBO).

**Secondary Hypotheses:** We will examine the feasibility, safety, tolerability, and potential efficacy of IN OT for relapse prevention in cocaine dependence. 2.1): Cocaine-dependent patients receiving IN OT who complete all 6 weeks of phase 2 will tally fewer cocaine using days than placebo patients who complete all 6 weeks. 2.2): Cocaine-dependent patients receiving OT who relapse will tally fewer cocaine using days than patients receiving placebo who relapse. Regression analysis will be implemented using those who complete (2.1) and those who relapse (2.2) to test the effect of OT on the secondary outcome (cocaine using days).

**Exploratory Aims:** We will investigate a) if the acute reduction in stress sensitivity with IN OT in Phase 1 or at the end of Phase 2 (repeat IN DDAVP challenge) is associated with a greater number of days of continued abstinence from cocaine in Phase 2; b) if there are gender effects on the primary outcomes.

## Description of Subject Population

### Sample #1

#### Specify subject population

cocaine-dependent sample

#### Number of completers required to accomplish study aims

50

#### Projected number of subjects who will be enrolled to obtain required number of completers

75

#### Age range of subject population

18-60

### Sample #2

#### Specify subject population

control sample

#### Number of completers required to accomplish study aims

50

#### Projected number of subjects who will be enrolled to obtain required number of completers

75

#### Age range of subject population

18-60

---

### **Gender and Ethnic Breakdown**

Based on our previous studies at the Substance Treatment and Research Service, it is expected that 50% of participants entering this trial will be African-American, 25% Hispanic-American, 20% Caucasian, and less than 5% Asian. Similar race/ethnicity statistics are found at the Division on Substance at the Albert Einstein College of Medicine. We expect gender percentages of 55% for men, and 45% for women. To establish our comparator control group, we will keep a table of demographic characteristics of cocaine-dependent samples.

### **Description of subject population**

Cocaine-Dependent sample: Men and women, aged 18 to 60, who meet DSM-IV criteria for current cocaine dependence, and who is seeking treatment. Cocaine-dependence has to be verified by at least one cocaine positive urine toxicology. The patients must use at least 4 days within a month, with at least weekly use. Binge patterned use can be considered if they occur at least 2x/month, and involved the use of at least \$200. The patients should read, speak and write english sufficiently to adequately consent to participate, and be able to adequately perform study procedures. They must be able to pass the scent test, a test that determines if their sense of smell is intact.

Control sample: Men and women, aged 18 to 60, without presents drug dependence. The patient should read, speak, and write english sufficiently to adequately consent, and be able to perform study procedures. They must be able to pass the scent test, a test that determines if their sense of smell is intact.

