**Create or insert table to describe the inclusion criteria and methods to ascertain them**

INCLUSION CRITERION	METHOD OF ASCERTAINMENT
1.Age 18 to 60.	MINI interview, self-report, ID confirmation
2. Meets DSM IV criteria for current cocaine	MINI Interview, self

dependence and is seeking treatment.	report
3. Displays at least one cocaine-positive urine toxicology during screening.	Urine Toxicology
4. Use of cocaine at least 4 days in the past month, with at least weekly use, or reports episodic binges of large amounts of cocaine (at least \$200) at least 2x/month.	Self report
5. Able to give informed consent and comply with study procedures.	MINI, Self-report, MSE
6. Can pass the blindfolded scent test recognizing the scent of cinnamon or coffee.	Scent test

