Study Assessments: (Table 1). **Physiological tests:** 1) *urine toxicology:* this will be estimated qualitatively at every visit by dipstick (Iscreen™, 9 drugs) which indicates the presence of cocaine, amphetamine, metamphetamine, cannabis, methadone, morphine, oxycodone, barbiturate, benzodiazepine. 2) *stress sensitivity testing:* as outlined in table 2, it is performed on two separate days, [in counterbalanced order.] Day 1: an endocrine challenge with IN DDAVP 80IU (de Goeij et al., 1991). After establishing baseline ACTH secretion, serum samples are taken at time points extending to 90 minutes. The DDAVP challenge is also repeated at the end of phase 2, to see if ACTH secretion is affected by 6 weeks of IN OT administration. Day 2 tests if pretreatment with IN OT treatment can acutely dampen the effect of DDAVP on ACTH secretion. After baseline is measured before and after IN OT, serum samples for ACTH are taken at time points extending to 90 minutes. Serum samples are spun, frozen at -20 Celsius, packed in dry ice, and shipped to the Nathan Kline Laboratory in Orangeburg, NY. 3) Medical monitoring: week 2,4,6: Na, K, Cl, CO3, spot cortisol, β-HCG for women. **Clinician Interviews:** 1) TLFB (Litten and Allan, 1992; baseline, each visit in phase 2). This is an adaptation of the alcohol TLFB, which estimates cocaine use in the past 30 days at baseline, and is then repeated at every visit with the aid of a calendar to obtain a day-by-day registry of cocaine use during phase 2. 2) CGI-O, (Guy, 1976; baseline, weekly during phase 2) the severity and improvement scales measure the overall clinical status of the subject and change from baseline. 3) BAS (Chaplin et al., 2010). This scale is used during stress sensitivity testing. Research staff rate participants on 13 items of behavior relating to arousal during the stress challenge. 4) Adverse event form is a check-list of side effects experienced by participants; 5) HamD, (Williams, 1988; baseline, each wk in phase 2). Estimates 25 depression symptoms. **Self reports:** 1) PSS (Cohen et al., 1983; baseline, weekly during phase 2) measures monthly situations in a subject's lives deemed stressful. Ten questions are scored between 0 (never) to 4 (very often). Modified, it will be administered weekly during phase 2, [and will include a open-ended question inquiring about any adverse life event in the past week.] 2) *Subjective ratings of cocaine craving, depression, anxiety, stress during stress testing (Likert scale 0 to 10, 10 = worse), performed during stress sensitivity testing.* 3) CCS (Weiss et al., 1997) 3-item questionnaire rating cravings for cocaine on a scale of 0 (none) to 9 (Strong).

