
3.3 Compensation and data management.

For phase 1, control participants will receive \$150 for their participation; cocaine-dependent patients will receive \$20/day, or will receive \$150 if they complete the whole week. [During phase 2, cocaine-dependent patients accumulate vouchers for completing all study procedures (Bringing home bottle, assessments, study visits).] Each visit with all study procedures completed will earn them \$5. They can also earn \$20 for each week of consecutive and complete participation. Transportation costs are covered (\$5/visit). Total earnings can reach \$450. StudyTrack, a software system for clinical trials will be used for data management.

3.4 Statistical Analysis:

3.4.1. Outcome measures: PHASE 1: **Primary outcomes:** 1) secretion of ACTH (continuous measure of area from the concentration-time curve (AUC) using trapezoid method, pg/mL/min). 2) subjective rating of cocaine craving, stress, depression, anxiety (continuous) 3) difference in ACTH secretion between IN DDAVP (day 1) and IN OT prior to IN DDAVP (day 2) (continuous measure); 4) difference in subjective rating of cocaine

craving, stress, depression, anxiety between IN VP (day 1) and IN OT prior to IN DDAVP (day 2; continuous, controlled for last day of use before entering Phase 1); **PHASE 2: Primary outcome:** 1) maximum number of consecutive abstinent days (continuous measure) ; **Secondary outcome:** 1) cocaine using days (continuous). **Covariates/Predictor Variables:** demographics, age, gender; cocaine data (TLFB, 30 days; IN vs. smoked).

3.4.2. Sample size: In PHASE 1, we will enroll a total of 100 participants: 1) Cocaine group (COC): Cocaine-dependent patients seeking treatment (n=50); 2) Control group (CON): Healthy matched controls (n=50), each matched demographically (see 3.1.1). In PHASE 2, we will randomize the 50 COC patients into two groups: 1) Oxytocin group (OT), n=25; 2) Placebo group (PBO), n=25. An independent statistician will perform, and an independent pharmacist will implement the randomization. Individuals will be stratified by route of cocaine use. The randomization will be balanced in blocks of random size 2 and 4 to prevent compromise of the blind.

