Primary Aim 2 [Phase 2]: The goal of primary aim 2 is to investigate the effect of OT on cocaine use after abstinence induction. **Primary Aim 2, hypothesis 1:** Cocaine-dependent patients receiving IN OT will display significantly more days of consecutive abstinence after abstinence induction compared with IN placebo at the end of the study. The effect of IN OT treatment (based on groups) on the primary outcome (maximum number of consecutive abstinence days for each patient) will be analyzed using generalized linear models (PROC GLIMMIX in SAS®) with main effect of randomization assignment (OT vs. PBO).

Secondary Hypotheses: We will examine the feasibility, safety, tolerability, and potential efficacy of IN OT for relapse prevention in cocaine dependence. 2.1): Cocaine-dependent patients receiving IN OT who complete all 6 weeks of phase 2 will tally fewer cocaine using days than placebo patients who complete all 6 weeks. 2.2): Cocaine-dependent patients receiving OT who relapse will tally fewer cocaine using days than patients receiving placebo who relapse. Regression analysis will be implemented using those who complete (2.1) and those who relapse (2.2) to test the effect of OT on the secondary outcome (cocaine using days).

Exploratory Aims: We will investigate a) if the acute reduction in stress sensitivity with IN OT in Phase 1 or at the end of Phase 2 (repeat IN DDAVP challenge) is associated with a greater number of days of continued abstinence from cocaine in Phase 2; b) if there are gender effects on the primary outcomes.

Power Analysis: **Primary aim 1:** With 50 cocaine dependent subjects and 50 matched controls, we have 50 matched pairs which give us at least 80% power to detect a significant difference between groups using 2-sided hypothesis test at a 5% level of significance for an effect size $\geq .41$. This is considered a small/medium effect size (Araya et al., 2006; Simeon et al., 2011), which are reasonable to expect based on the existing literature. **Primary aim 2:** In Phase 2, we randomize 50 participants into 2 groups (25 in PBO and 25 in OT). The comparison will achieve at least 80% power (testing 2-sided hypothesis of difference at 5% significance) when detecting an effect size ≥ 0.8 . This is a medium effect size that we based on existing relapse studies in cocaine dependence (Back et al., 2010).

Primary outcome:

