The primary outcome was maximum number of consecutive cocaine abstinent weeks. Cocaine use was determined using urine toxicology and TLFB self-report. In a given week, cocaine use was defined as positive if any urine toxicology tests or TLFB self-report was positive (regardless if urine toxicology was negative or missing). Cocaine use was defined as negative if both urine toxicology and self-report were negative or if urine toxicology was missing, the self-report was negative. Cocaine use status was defined as missing if both urine toxicology and self-report were missing. Wilcoxon rank-sum tests were used to examine differences in maximum number of consecutive cocaine abstinent weeks by medication group.

Twenty-six cocaine patients were randomized to 6 weeks of Oxytocin (n=15) or Placebo (n=11). The median (IQR) of the maximum number of consecutive abstinent weeks was 1.0 (1.0 to 1.0) for the OT group and 1.0 (1.0 to 2.0) for the PBO group. The Wilcoxon rank-sum test was not significant, there was no effect of treatment arm on the maximum number of consecutive abstinent weeks ($W = 144.5, p = .67$).

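### The Phase 2 primary outcome (longest abstinent run) depends on each patient's usual gap between uses, and no baseline-use covariate is fixed in advance, so precision and protection against chance imbalance are forgone

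*Protocol*

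**What the plan says.** **Who is enrolled.** The protocol's description of the cocaine-dependent sample asks for use on four or more days a month "with at least weekly use. Binge patterned use can be considered if they occur at least 2x/month". Inclusion criterion 4 admits the same two patterns. The first is regular use: "Use of cocaine at least 4 days in the past month, with at least weekly use", with no ceiling. The second is episodic binges at least twice a month.

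**What is measured.** SAP 3.4.1 gives the Phase 2 primary outcome as "maximum number of consecutive abstinent days (continuous measure"). The SAP's closing section on the primary outcome counts weeks instead: "The primary outcome was maximum number of consecutive cocaine abstinent weeks". Neither is referred to the patient's own pre-treatment run.

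**How it is analysed.** Under Primary Aim 2, the SAP specifies a generalized linear model "with main effect of randomization assignment (OT vs. PBO"). SAP 3.4.2 stratifies randomization by route of use only. SAP 3.4.1 lists as covariates "demographics, age, gender; cocaine data (TLFB, 30 days; IN vs. smoked"), and SAP 3.4.4 lets a covariate in only if it proves to affect the outcome. No test, threshold or summary of the TLFB data is given. The closing section reports a Wilcoxon rank-sum test by arm and describes no adjustment.

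**What is available.** The TLFB is an instrument "which estimates cocaine use in the past 30 days at baseline" (SAP, Study Assessments). The protocol's end-of-study responder rating (Study Procedures, Phase 2, item 11) does compare use with the prior 30 days. The primary outcome does not.

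**The concern.** A longest run of abstinent days is tied mechanically to how often the patient uses. A patient who binges twice a month and changes nothing still has a run of about two weeks. A near-daily user who improves a great deal may never reach that. Part of the between-patient spread in the primary score is therefore habit and not relapse prevention.

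Two things are at stake in a trial planned at 25 per arm, with 26 patients in all reported as randomized (15 v 11). One is precision, because spread that a baseline measure could explain stays in the error term. The other is chance imbalance, because a few more infrequent users in one arm move the estimate and nothing in the named model corrects for it. A covariate rule that looks at the data first also leaves an analyst's choice inside the primary analysis.

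**Working it through.** **1. The plan's own figure.** Inputs from the SAP Power Analysis: 25 per arm, standardized effect d = 0.8, two-sided 5%.

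- Normal approximation: d × √(n/2) = 0.8 × √12.5 = 2.828; power = Φ(2.828 − 1.960) = 80.7%.
- Required n per arm = 2 × (1.960 + 0.842)² / 0.8² = 24.5, so 25.
- Exact noncentral t, 48 df: 79.1%.

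The stated 80% reproduces.

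**2. Does the outcome track habit?** Longest run over 42 days with evenly spaced use:

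| Use pattern | Longest run (days) |
|---|---|
| every 14 days | 13 |
| every 7 days | 6 |
| every 4 days | 3 |
| every 2 days | 1 |

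So an unchanged fortnightly user scores 13, while a daily user who improves to every fourth day scores 3. With use placed at random, an unchanged user at 2 days per 30 averages a run of 23 days. A user at 25 days per 30 averages 6 after halving use and 11 after a 75% cut. The unchanged infrequent user has the longer run with probability 99.5% and 90% respectively.

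**3. Does a count of use days separate the patterns?** Only partly. A once-a-week user and a patient with two 2-day binges both show about 4 use days in 30. Their longest gaps, evenly spaced, are about 6 and 13 days.

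**4. Size in power.** The documents give no SD in days, no mix of use patterns and no correlation with baseline, so these are assumptions: near-daily/weekly/binge mixes of 33/33/33, 60/20/20 and 80/10/10, and other outcome SD of 8 or 12 days. Under these, the baseline longest run explains about 7-25% of outcome variance (R²), and days of use about 6-18%. If 0.8 is in total-SD units, the adjusted effect is 0.8 / √(1 − R²):

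| Covariate | R² | Effect | Exact-t power, 25 per arm |
|---|---|---|---|
| none | 0 | 0.800 | 79.1% |
| days of use, low | 0.06 | 0.825 | 81.6% |
| baseline run, low | 0.07 | 0.830 | 82.0% |
| days of use, high | 0.18 | 0.883 | 86.4% |
| baseline run, high | 0.25 | 0.924 | 89.3% |

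The covariate's degree of freedom (47 instead of 48) takes off less than 0.1 point. The run adds about 0.4 to 2.8 points over days of use.

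**5. If 0.8 were instead an effect among patients of like frequency.** The unadjusted effect becomes 0.8 × √(1 − R²). At R² = 0.2 this is 0.716, unadjusted power (normal) is 71.6%, and 80% needs 31 per arm. At R² = 0.5 it is 0.566, 51.6% and 50 per arm. The SAP does not say which meaning applies.

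**6. Chance imbalance.** Take typical unchanged runs of 3 days (use on five days a week) and 14 days (two 2-day binges per 30 days), both assumed patterns. Three near-daily users replaced by three bingers in one arm shift that arm's mean by 3 × (14 − 3) / 25 = 1.3 days. The target effect is at least 0.8 × 8 = 6.4 days at the smaller assumed SD.

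**7. Type I error.** In simulated trials without a treatment effect, the t-test, the rank-sum test and the baseline-adjusted models all rejected in about 4-6% of runs.

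**The case against.** The strongest reply is that the SAP already holds the remedy. It lists "cocaine data (TLFB, 30 days; IN vs. smoked") as a covariate, and if that is used, most of the available gain follows. A reader might infer that the covariate list shuts out a measure of the usual gap. It does not: a longest run of non-use, or a binge flag, is itself 30-day TLFB cocaine data. This part of the reply stands. What remains is that the summary is undefined and its entry depends on the data.

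A reader might also infer that the planned 80% power is lost. The documents do not support that. If 0.8 is measured against the total SD, the planned power roughly holds without adjustment, and adjustment only adds to it. Loss follows only under the within-frequency meaning in step 5, which the SAP does not state.

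The simulations also carry pre-treatment habits through Phase 2. In the trial, abstinence induction comes first, patients who cannot comply with it do not proceed, and those who do attend three times a week and receive compliance therapy. Habit may therefore explain less than assumed. The result depends on spacing too: if the weekly user's day varies within the week, the median run is about 10 days and not 6 or 7, which narrows the contrast with the binger. The share of bingers is unknown. The reported runs in weeks are tightly bunched (medians 1.0; IQR 1.0-1.0 and 1.0-2.0). These points limit the size of the concern but do not remove it.

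**Conclusion.** The point holds as one of precision and chance imbalance. Eligibility spans near-daily use to two binges a month, the outcome is an absolute run, and no text guarantees that baseline use enters the primary analysis. It is not a bias: randomization protects the comparison, and the simulated type I error is unaffected.

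Under the stated assumptions, a prespecified baseline-use covariate lifts power from 79% to about 82-86% (days of use) or 82-89% (longest baseline run). Most of that comes from fixing any baseline-use covariate; the choice of the run over the count is worth roughly 0 to 3 points. Simulations in which use frequency carries through entirely give a baseline R² of about 0.7 and much larger gains. They are best read as illustrative, because they ignore abstinence induction. The true size cannot be fixed from the documents. The change is worth making because it is cheap and removes a data-driven choice from the primary analysis.

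**What to change.** - In SAP 3.4.1 and the Primary Aim 2 model, replace the conditional rule for baseline use with one fixed covariate, included for every patient whatever the data show. The preferred choice is the longest run of consecutive non-use days in the 30-day baseline TLFB, transformed if skewed, with the transformation settled before unblinding.
- If baseline days are not held day by day, use days of use, or the regular/binge pattern needed to judge inclusion criterion 4.
- If a rank test is the primary analysis, use the stratified (van Elteren) version by that pattern.
- In the Power Analysis, state whether 0.8 is in total-SD units or conditional on baseline use.

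The cost is SAP wording and one variable derived from data already collected, with no change to visits or treatment. The downsides are one degree of freedom and reliance on retrospective self-report. Because the SAP's closing section already reports the comparison, an adjusted analysis of these data would be post hoc and should be labelled a sensitivity analysis.
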